11.4 Exploratory Objectives

- To evaluate preoperative, intraoperative and postoperative factors that affect the efficacy of the amiodarone dosing strategy in achieving NSR at 24 hours, ICU discharge and hospital discharge, multiple variable logistic regression modeling will be constructed using any significant variable discovered in the bivariate analysis.
- Evaluate preoperative, intraoperative and postoperative factors that affects the safety profile of the repeated amiodarone bolus dosing regimen, multiple variable logistic regression modeling will be constructed using any significant variable discovered in the bivariate analysis.

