3.3 Exploratory Objectives

The exploratory objectives of this study are:

- Evaluate preoperative, intraoperative and postoperative factors that affect the efficacy of the amiodarone dosing strategy in achieving NSR at 24 hours, ICU discharge and hospital discharge.
- Evaluate preoperative, intraoperative and postoperative factors that affects the safety profile of the repeated amiodarone bolus dosing regimen.

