10.3 Postoperative data

- Date/time of ICU admission
- Date/time of extubation

- Date/time of ICU discharge
- Date/time of hospital discharge
- Vasopressor (norepinephrine, vasopressin) use at ICU admission
- Inotrope (dopamine, epinephrine, milrinone, dobutamine) use at ICU admission
- Pacemaker use at ICU admission
- Date/time of first AF
- Presence of rapid ventricular response with first AF
- Heart rate at time of AF diagnosis
- Heart rate at initiation of study group treatment (initial amiodarone bolus)
- Hourly heart rate for 24 hours, beginning at start of study group treatment
- Date/time of study randomization
- Date/time of first study drug administration
- Total number of amiodarone boluses administered
- Restoration of normal sinus rhythm by ICU discharge
- Restoration of normal sinus rhythm by hospital discharge
- Date/time of normal sinus rhythm
- Total number of stable AF episodes (excluding initial episode) prior to ICU discharge
- Total number of stable AF episodes (excluding initial episode) prior to hospital discharge
- Presence of hypotension (SBP < 90 mmHg or increase in vasopressor infusion by 1.5x to achieve SBP > 90 mmHg) after amiodarone therapy during amiodarone IV load period
- Severity of hypotension after amiodarone therapy during amiodarone IV load period
 - Mild: No intervention needed
 - Moderate: Hypotension resolved after fluid bolus

- Severe: Hypotension requiring vasopressor or inotropic therapy
- Very Severe: Hypotension requiring multiple vasopressor or inotropic therapies
- Presence of bradycardia (HR <60 beats per minute) after amiodarone therapy during amiodarone IV load period
- Presence of conduction abnormality during amiodarone IV load period
- Severity of conduction abnormality during amiodarone IV load period
 - Mild: No intervention
 - Moderate: Temporary pacemaker required for ≤ 12 hrs
 - Severe: Temporary pacemaker required for 12-48 hrs
 - Very Severe: Temporary pacemaker required for ≥ 48 hrs or permanent pacemaker required
- Presence of pulmonary fibrosis related to amiodarone therapy
- Severity of pulmonary fibrosis related to amiodarone therapy
 - Mild: No intervention needed
 - Moderate: Discharged on oxygen at night only
 - Severe: Discharged on continuous oxygen
 - Very Severe: Discharged on mechanical ventilation or patient death due to pulmonary fibrosis

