11.1 Baseline and demographic data

To describe baseline and demographic data, preoperative, intraoperative and postoperative data will be summarized and compared between patients randomized to the CDR and RBDR groups. Binomial and categorical data will be described as number (N) and percentage. Continuous data will be analyzed for normality. Data will be tested for normality using the Shapiro-Wilk test. Normal data will be described by the mean and standard deviation; whereas, non-normal data will be described by the median and interquartile range. Nominal data will be compared with the Fischer's Exact test or the Chi-Square test, as appropriate. Normal continuous data will be compared with the 2-tailed, student t-test. Non-normal continuous data will be compared with the Mann-Whitney U test. All results with p<0.05 will be considered significant.

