# 1.4 Exploratory Objectives

- To evaluate preoperative, intraoperative and postoperative factors that affect the efficacy of the amiodarone dosing strategy in achieving NSR at 24 hours, ICU discharge and hospital discharge, multiple variable logistic regression modeling will be constructed using any significant variable discovered in the bivariate analysis.
- Evaluate preoperative, intraoperative and postoperative factors that affects the safety profile of the repeated amiodarone bolus dosing regimen, multiple variable logistic regression modeling will be constructed using any significant variable discovered in the bivariate analysis.

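### The exploratory regression models screen predictors by significance and admit on-treatment variables, so they can describe predictors of conversion but are not set up to show what modifies the effect of the regimen

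*Protocol*

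**What the plan says.** Protocol 3.3 sets two exploratory objectives. The first is to "Evaluate preoperative, intraoperative and postoperative factors that affect the efficacy of the amiodarone dosing strategy in achieving NSR at 24 hours", and also at ICU and hospital discharge. The second, repeated in Protocol 11.4, concerns "factors that affects the safety profile of the repeated amiodarone bolus dosing regimen".

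The method for both is one clause in Protocol 11.4: "multiple variable logistic regression modeling will be constructed using any significant variable discovered in the bivariate analysis". SAP 1.4 has the same text, with the model again built "using any significant variable discovered in the bivariate analysis". Neither document lists the model terms, defines the bivariate analysis, names the safety outcome to be modelled, or limits the number of predictors. The only significance threshold is in Protocol 11.1: "All results with p<0.05 will be considered significant". No multiplicity adjustment is given.

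The candidate pool is the data list in Protocol 10.1 to 10.3. The postoperative part includes "Total number of amiodarone boluses administered", hourly heart rate from the start of study treatment, and hypotension and bradycardia during the IV load. It also includes items that precede randomisation: vasopressor, inotrope and pacemaker use at ICU admission, rapid ventricular response with first AF, and heart rate at AF diagnosis. None is excluded.

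**The concern.** On its natural reading, the efficacy objective asks what makes the dosing strategy work better or worse, which is a question of effect modification. A model made of whichever variables pass a significance screen answers a different question: who converts, whatever the regimen. A factor can predict conversion strongly and leave the regimen effect unchanged. A factor that reverses the regimen effect may show no overall association with conversion.

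The open door to postoperative variables adds a second problem. Under Protocol 9.2, extra boluses are specified only in RBDR and only after sustained tachycardia. Bolus count therefore depends on the assigned arm and on how the patient is responding, and it is not a baseline factor. In a safety model, hypotension and bradycardia would be both outcomes and eligible predictors.

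Followed as written, the analysis can report chance findings and consequences of treatment as factors that affect efficacy or safety.

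**Working it through.** The plan has no figure to reproduce: Protocol 11 says that no sample size calculation was done, and the exploratory section gives no variable or event counts. The inputs taken from the documents are 60 randomised patients (30 per arm), a possible extension to 80, and a 0.05 threshold. All conversion rates below are assumptions.

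**1. Number of candidates.** Protocol 10.1 gives 10 items (five demographics and five others) and Protocol 10.2 gives 11, so 21 before any postoperative item. Seven of the 11 intraoperative items are timestamps that reduce to a few durations, and height, weight and body mass index overlap. A range of 10 to 30 effective candidates is reasonable.

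**2. Chance selection.** For k independent null candidates, P(at least one enters) = 1 − 0.95^k, and the expected number is 0.05k.
- k = 10: 40%, expected 0.5
- k = 20: 64%, expected 1.0
- k = 30: 79%, expected 1.5

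This is for one outcome. The plan names three time points for sinus rhythm, plus safety.

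**3. Model capacity.** Using the conventional guide of 10 events per parameter, capacity is the smaller outcome group divided by 10.
- 50% converting: 30/10 = 3.0 parameters at n = 60, 40/10 = 4.0 at n = 80
- 70% converting: 18/10 = 1.8, and 24/10 = 2.4
- 80% converting: 12/10 = 1.2, and 16/10 = 1.6

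Within the 30 RBDR patients, an event affecting 50%, 30% or 20% gives 15, 9 or 6 events, so 1.5, 0.9 or 0.6 parameters.

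**4. Does the screen find effect modifiers?** This was simulated at n = 60 with a binary factor at 50%, screening the factor against conversion by chi-square or Fisher at p<0.05, and comparing with a test of arm-by-factor interaction.
- Purely prognostic factor (conversion 35% to 45% in one stratum, 75% to 82% in the other; arm odds ratio about 1.52 in both): passes the screen 87% of the time; interaction test positive 3%.
- Strong qualitative modifier (40% to 80% in one stratum, 80% to 40% in the other): passes the screen 2.6% of the time; interaction test positive 88%.
- Milder modifier (no effect in one stratum, 50% to 80% in the other): 21% and 22%.

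The first two cases are chosen to show the contrast. In the third, the two approaches detect the factor about equally often.

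**5. Adjusting for bolus count.** In an illustrative simulation, an unmeasured resistance drives both boluses and non-conversion, and bolus count itself has no effect. The arm odds ratio is 1.67 unadjusted and 3.18 with bolus count in the model, against a built-in conditional value of e^0.6 = 1.82. Each bolus appears to reduce the odds of conversion (odds ratio 0.69). A different mechanism would push the other way: if the extra boluses carry the benefit, adjusting for them removes part of the arm effect.

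**6. What an interaction term can deliver.** With four equal cells of n/4, the interaction is the difference between two log odds ratios, and SE = √Σ 1/[(n/4)·p(1−p)].
- 50% to 70% against no effect, n = 60: estimate ln(0.7/0.3) = 0.847, SE = √(3/3.75 + 1/3.15) = 1.057, power 13% (15% at n = 80).
- 50% to 80% against no effect, n = 60: estimate 1.386, SE = √(3/3.75 + 1/2.4) = 1.103, power 24% (31% at n = 80).
- Ratio of odds ratios detectable with 80% power, all cells near 50%: exp[(1.96 + 0.8416) × √(4/3.75)] = about 18 at n = 60, and about 12 at n = 80.

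**The case against.** **The model is under-described, so silence should not be read as specification.** This stands in part. A reader might infer that the plan rules out an interaction or that arm will drop out. Neither is stated: the terms are simply not listed. The bivariate analysis might even mean the between-arm comparisons of Protocol 11.1, in which case arm would be the exposure and not a screened candidate. That reading does not rescue the method. Protocol 11.1 compares postoperative data between arms too, so variables that the regimen itself shifts would be especially likely to enter.

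**The objectives can be read more modestly.** This also stands. The safety objective names only RBDR and can be read as a within-arm description, which needs no interaction term. The efficacy objective could mean predictors of reaching sinus rhythm. It would therefore be too strong to say that the models can identify nothing useful.

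**The bolus argument has no fixed direction.** Accepted. Extra boluses are triggered by heart rate, not by failure to convert as such. The documents do not support the inference that bolus count would necessarily appear to cause failure.

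**The error rates are idealised.** Accepted. They assume independent null tests at exactly 5%. Correlated variables and the conservatism of Fisher's test would change them, and they describe entry into the model, not survival after adjustment.

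**The remedy is itself underpowered.** True. Arm, factor and interaction are three parameters, which is the limit at 50% conversion and n = 60 and beyond it at 70% or 80%. That is a reason to present estimates cautiously, not to keep the screen.

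**It is only exploratory.** That excuses low power. It does not excuse a stated method aimed at another question or one that admits consequences of treatment as predictors.

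**Conclusion.** The point holds in a limited form. The explicit selection rule and the unrestricted admission of postoperative variables are flaws in the stated method. The missing arm and arm-by-factor terms are omissions. The models can give prognostic associations with conversion, but they are not set up to show what modifies the effect of RBDR against CDR.

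The 40% to 79% figure rests on an assumed 10 to 30 independent null candidates. The 3.0, 1.8 and 1.2 parameters rest on assumed conversion rates and a rule of thumb. The bias from on-treatment variables is real in principle, with its direction and size undetermined. Importance is modest: no primary or secondary conclusion, sample size or stopping decision depends on these analyses.

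**What to change.** Amend Protocol 11.4 and SAP 1.4 together, and Protocol 3.3 where the objective is reworded:

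- Replace the bivariate screen with two or three named pre-randomisation factors. Preoperative beta-blocker use and ejection fraction are examples. Postoperative items recorded before randomisation, such as rapid ventricular response at first AF or vasopressor use at ICU admission, remain eligible.
- Always keep arm in the efficacy model. Report each arm-by-factor interaction in a separate model, as an odds ratio (strictly, a ratio of odds ratios) with 95% CI.
- Label these results hypothesis-generating, and state that a null interaction is not evidence of no modification.
- For RBDR safety, name the outcome and describe the same factors within that arm only.

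Alternatively, reword the efficacy objective as predictors of conversion, still restricted to pre-randomisation variables and with arm retained.

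The cost is wording in both documents. All the factors suggested are already collected under Protocol 10.1 and 10.3. The downside is that fewer variables are examined and the interaction estimates will be imprecise.

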12. RESOURCES

All usual care for a post-operative surgical patient will be provided to enrolled patients by hospital staff. Emergency medical equipment, medications, and supplies will be at the physician's disposal should the patient have an acute, unexpected reaction to study drugs. The anesthesiology critical care team will be responsible for ordering study-related drugs, according to standard of care protocols, and for responding to unexpected reactions to study drugs. Evaluations, examinations, and tests will be ordered by the cardiovascular surgery, anesthesiology critical care medicine or other consultants according to standard of care protocols. Research staff of the Anesthesiology Research Program will be responsible for randomizing enrolled patients, communicating group assignment to the anesthesiology critical care medicine team, monitoring study-related complications and adverse events, and collecting study-related data.

13. POTENTIAL RISKS

Because this study compares 2 amiodarone dosing strategies already used in the proposed study population, there are no specific study-related risks of amiodarone administration. Regardless of whether they are enrolled in this study, patients with persistent, postoperative stable AF will receive amiodarone IV bolus and infusion, unless they have a contraindication to its uses. These patients may receive either the CDR or the RBDR, based entirely on clinician preference. In this study, we are comparing the efficacy and safety of the currently used dosing regimens.

The primary risk of this study is, therefore, only a risk of breach of confidentiality.

14. SAFETY PRECAUTIONS

14.1 Risks from Breach of Confidentiality

All enrolled patients will be given a 3-digit study identification number (SID) at the time of study enrollment. All patient data will be identified only with the SID and will be maintained only on the REDCap online database. All informed consent records will be scanned in the Department of Anesthesiology, stored on the REDCap online database, and then immediately destroyed in the Department of Anesthesiology in a paper shredder.

15. BENEFIT VERSUS RISK

Patients enrolled in this study may receive a direct benefit from their enrollment or randomization to either group. The risk in this study will be the same across both groups.

16. AVAILABLE ALTERNATIVE TREATMENT

For patients that do not consent to enrollment in this study, they will receive current standard of care treatment for stable, postoperative AF, as determined by the cardiovascular surgery and/or anesthesiology critical care medicine teams.

17. RESEARCH MATERIALS, RECORDS, AND PRIVACY

The research team maintains the right to keep, preserve, use and dispose of the findings from this study. Research records from this study will be maintained in a confidential manner; subjects' names will not be associated with any study procedures or published results. All data will be used for the purpose of research. All data will be retained for six years after study closure. Electronic records will be deleted at the specified times according to UK policy A13-050.

18. CONFIDENTIALITY

All electronic data containing identifiers will be stored on the secure REDCap database. Only designated study personnel will have access to data files. Investigational records for this study will be maintained in a confidential manner; subjects' names will not be associated with any published results nor used for any purpose. All data will be used for the purpose of research. All data will be retained for six years after study closure.

19. PAYMENT

No financial compensation will be provided to subjects.

20. COSTS TO SUBJECTS

The patient, the patient's insurance company, Medicare, or Medicaid will be responsible for the costs of all care and treatment that they receive during this study, including the cost of the study drug. Because both amiodarone dosing regimens are currently used, the cost of the study drug and other costs are considered medically reasonable and necessary and will be part of the care the patient would receive if they did not take part in this study.

21. DATA AND SAFETY MONITORING

Each subject will be monitored for adverse events (AE) and serious adverse events (SAE) by the PI and/or a member of the research team. Because hypotension and conduction system abnormalities are expected, reversible and treatable complications of amiodarone, they will be monitored but will only be considered AE if they reach "severe" criteria and will only be considered as SAE if they reach "very severe" criteria. Other known complications of amiodarone therapy will be reported as AE or SAE, as appropriate. All AE and SAE will be reported to the IRB per IRB guidelines.

The PI and co-investigators will review the AE and SAE reports after the first 10 patients have completed the research protocol to evaluate patient safety. If, after the first 10 patient have been evaluated, there were no AE or SAE reported, the PI and clinical co-investigators will continue to review the AE/SAE reports after every additional 20 patients have completed the protocol. If, during these periodic reviews, there are reported AE or SAE, the PI and clinical co-investigators will consider whether to continue patient enrollment and study procedures based on an assessment of benefit versus risk. The PI will have the responsibility, in consultation with the

clinical co-investigators, to decide whether to continue the study at each 20-patient interim safety analysis. The PI will inform the IRB if study procedures will be terminated.

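### The hypotension and conduction grades have no class for death or cardiac arrest, yet AE and SAE status depends only on the grade, so some fatal events are under-classified and others cannot be graded

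*Protocol*

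**What the plan says.** Protocol section 21 treats two complications separately from all others. It gives the reason that "hypotension and conduction system abnormalities are expected, reversible and treatable complications of amiodarone". On that basis, "they will be monitored but will only be considered AE if they reach 'severe' criteria", and they become serious only at the next grade up: the sentence runs on from the severe "criteria and will only be considered as SAE if they reach" the very severe level. The sentence that follows covers the rest: "Other known complications of amiodarone therapy will be reported as AE or SAE, as appropriate".

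The grades are defined in section 10.3. Hypotension is graded by what was needed to treat it: nothing, a fluid bolus that resolved it, a vasopressor or inotrope, or several such agents. The third class reads "Severe: Hypotension requiring vasopressor or inotropic therapy". Conduction abnormality is graded by whether and for how long a pacemaker was needed, for example "Moderate: Temporary pacemaker required for ≤ 12 hrs". The top class is pacing for 48 hours or more, or a permanent device. Neither scale mentions death or cardiac arrest. The pulmonary fibrosis scale in the same list does: "Very Severe: Discharged on mechanical ventilation or patient death due to pulmonary fibrosis".

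The grades have two uses. Section 21 has the investigators review AE and SAE reports after the first 10 patients and then, if there were none, after every further 20. Protocol section 11.3 and SAP section 1.3 compare the severity classes between arms with Somers' D.

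**The concern.** Each scale measures treatment intensity or duration, not outcome. For conduction events, death also cuts short the pacing time that sets the grade, so an early death tends to lower it. Because section 21 uses the word only, there is no second route by which the outcome itself could make the event serious.

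What is at stake is the formal safety record of a trial whose experimental arm allows up to six boluses in 24 hours (section 9.2). The two complications affected are the ones section 21 itself expects from amiodarone. Reported AEs and SAEs are what prompt the investigators to consider whether to continue. A fatal event that the rule classes as neither would count as no event for that purpose. One classed as an AE would reach the review, but without serious status.

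**Working it through.** The main check needs no arithmetic. Take a fatal event of each kind, apply the section 10.3 definitions literally, then apply the section 21 thresholds.

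| Fatal event | Grade under 10.3 | Status under 21 |
|---|---|---|
| Conduction, paced 12 h or less | Moderate | Neither AE nor SAE |
| Conduction, paced 12 to 48 h | Severe | AE, not SAE |
| Conduction, paced 48 h or more, or permanent device | Very Severe | SAE |
| Arrest treated without pacing | No class fits | Undefined |
| Hypotension, one vasopressor or inotrope | Severe | AE, not SAE |
| Hypotension, several agents | Very Severe | SAE |
| Hypotension, fluid only, not resolved | No class fits | Undefined |

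Fatal hypotension cannot be Moderate, because that class requires the episode to have resolved. It does not sensibly fit Mild either, because that class is for episodes that needed no intervention.

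Next, the text was searched for a rule that overrides the grade. The catch-all sentence in section 21 is limited to other complications. Reporting to the IRB under its guidelines applies to events already classed as AE or SAE. Section 10 says collection is not limited to the list and includes adverse events, but it does not name death. The list in 10.3 has ICU and hospital discharge times, and mentions death only under pulmonary fibrosis. No override was found.

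The effect on the severity comparison can be sized with a hypothetical example; the event counts are assumptions, not figures from the plan. Take 30 patients per arm, as planned. Each arm has 2 mild conduction events. RBDR also has 2 deaths within 12 h of pacing (Moderate = 2), and CDR has 2 survivors paced for 24 h (Severe = 3). With group as the independent variable, D = (pairs with RBDR higher − pairs with RBDR lower) / all between-arm pairs.

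- Patients with events only, as graded: CDR {1,1,3,3}, RBDR {1,1,2,2}. RBDR is higher in 4 pairs, lower in 8 and tied in 4. D = (4 − 8)/16 = −0.25.
- Same patients, deaths scored 4: RBDR is higher in 8, lower in 4 and tied in 4. D = (8 − 4)/16 = +0.25.
- All 30 per arm, no event scored 0: there are 30 × 30 = 900 pairs. The 26 event-free patients in each arm add 26 × 4 = 104 pairs in each direction, which cancel. D = −4/900 ≈ −0.004 as graded, and +4/900 ≈ +0.004 with deaths scored 4.

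The sign reverses either way. The size depends on the denominator, which the SAP does not state.

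**The case against.** The strongest reply is that section 21 gives its reason. Lower grades are exempt because such events are expected, reversible and treatable. A death is not reversible, so a sensible reader would place it outside the exemption. That is a fair reading of intent, but the operative words tie status to grade alone and nothing in the available text says otherwise. The IRB guidelines that section 21 refers to, and protocol section 22, were not available for this review. Either might contain a general rule on deaths. If so, the gap would narrow, but section 21 would then conflict with that rule and would still need rewording.

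A second reply is that a death would hardly go unnoticed. The trial is open-label at one center, patients are continuously monitored through the IV load, research staff monitor complications (section 12), and the reviewers are the investigators themselves. This stands. A reader might infer that deaths would disappear from view, and the documents do not support that. The defect is in formal classification.

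A reader might also infer that any fatal event on either scale can be graded Mild or Moderate and so escape reporting. The wording of the hypotension classes rules this out, as shown above. A fatal block graded Mild would require that nothing at all was done, which is strained in monitored patients. Even the clearest case, death within 12 hours of pacing, depends on reading the pacing requirement as ended by death.

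Finally, the ±0.25 is a constructed contrast of 4 against 4 patients. That criticism stands, and the point does not rest on it.

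**Conclusion.** The point holds as a fault in the classification rule. Applied literally, it leaves one kind of fatal event (a conduction event paced for 12 hours or less) as neither AE nor SAE. It classes two others as AE but not SAE: a fatal conduction event paced for 12 to 48 hours, and fatal hypotension on one agent. It gives no grade to at least two more. The fibrosis scale shows that the authors accept death as a top-class outcome, so its absence from the two scales that control AE and SAE status is an inconsistency within section 10.3.

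Such deaths may be rare among the 60 to 80 patients to be randomized. The case for change is that the rule gives the wrong answer if one occurs, in the reports on which the safety reviews depend.

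The analysis consequence is secondary. An early death can rank below a survivor who was paced for longer, but with all randomized patients included the example moves Somers' D only from about −0.004 to +0.004. A reader might infer a material reversal of the safety result, and these figures do not support that. The primary outcome and the bradycardia incidence comparison are not affected.

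The conclusion assumes a literal reading of section 21 and that no unseen text overrides it.

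**What to change.** Three changes, all to classification and data capture and none to treatment:

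- In section 10.3, add death or cardiac arrest due to the event to the Very Severe class of both the hypotension and the conduction scale, in line with how the fibrosis scale treats death.
- In section 21, state that a fatal or life-threatening event is an SAE whatever its grade.
- In section 10.3, add an item for in-hospital death with date, time and cause.

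The severity comparison then ranks event-related deaths in the top class without any change to the statistical method. The SAP should also say whether Somers' D uses all randomized patients or only those with events. The cost is a few sentences and one data item. The downside is that a few more events may be reported as SAEs.
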